3.2 Primary Study Endpoints

Feasibility and acceptability of imaging college-age participants administered Adderall or placebo.

4. Subject Selection and Withdrawal

4.1 Inclusion Criteria

- Age (18-24)
- College student with at least average IQ
- Willingness to standardize caffeine intake to 100mg on day of study

4.2 Exclusion Criteria

- Diagnosis of ADHD
- First degree relative with ADHD
- Unwillingness to comply with caffeine specifications
- Regular use of Adderall
- Pregnant/breastfeeding
- History of substance use disorders
- Illicit stimulant use within the last year
- Contraindications to stimulants (i.e., tics, Tourette's, cardiac disease, hypertension)
- Uncontrolled medical illness
- Active contagious infection

4.3 Study Recruitment and Screening

Advertisements posted around campus will include tear-off slips of paper with contact information. The study investigators have been able to recruit healthy controls in this age group in previous studies of a similar nature without going to TV or radio advertisements. A telephone pre-screen interview will be designed to capture the most obvious exclusion criteria so that potential screen failures can be eliminated prior to an office visit.

Self-referred potential subjects will have a pre-screen telephone interview. If self-referred potential subjects meet criteria from this pre-screen telephone interview, a screening appointment will be scheduled.

Screening Appointment (1-2 hours): During the consent process, the purpose of the study, its risks and benefits, the rights of the participants, and what will be required of participants will be discussed. The participants will be given time to ask questions and have their questions answered by trained research staff. A pregnancy test will be obtained for all non-sterile female participants and a urine drug screen will be obtained for all participants at the screening interview. Positive results on either will result in immediate disqualification from the study. Results will be read

prior to giving any medication to a subject. These procedures will not be repeated during the study unless considered clinically necessary based on history or signs and symptoms at the discretion of the study physicians. Participants will review the MRI safety questionnaire to ensure that it is safe for them to be scanned. Participants will then fill out a demographics sheet, MRI Safety Questionnaire, Prescription Stimulant Expectancies Questionnaire (PSEQ-II), and an ADHD screener, the Adult Self-Report Scale (ASRS) Symptom Checklist. Medical and psychiatric history will be reviewed. The absence of an ADHD diagnosis will be confirmed by a physician investigator.

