4.4 Early Withdrawal of Subjects

4.4.1 When and How to Withdraw Subjects

Students will be informed they may withdraw from the study at any time, for any reason, before it is completed. They will be informed that their participation will not affect their class standing or grades at UAB. They will not be offered or receive any special consideration if they take part in the research. Employees will be informed that taking part in the research is not part of their UAB duties and refusing to be a part of the study will not affect their job or relationship with UAB. They will not be offered or receive any special job-related consideration if they take part in this research.

5. Study Drug

Dextroamphetamine-amphetamine & Placebo

6. Study Procedures

Study Appointment (2-3 hours): Pulse and blood pressure will be measured before medication is administered. If pulse and blood pressure are within acceptable limits, medication will be administered. A potential side effect checklist (attached) will be reviewed after the period of time in which medication effects would become active. Any reported side effects will be addressed prior to continuation of the session. The MRI safety questionnaire will be reviewed and signed at each scanning visit. This questionnaire will be filed at the CINL. Any abnormal findings will be discussed with physician investigator who will determine if the subject is fit to participate in the study.

The participant will be given either a placebo or Adderall depending on randomization. Each participant (N = 4) will either be told that he/she is receiving Adderall or placebo, as indicated on pre-labeled medication bottles to preserve the double-blind nature of the study. The participant will either receive medication or placebo as they are informed, not receive medication when they believe they are receiving medication, or will receive medication when they believe they are not receiving medication. This will allow for measurement of expectancy, which is a core measure for this study. This study design makes the comparison of cognitive performance based on actual versus perceived benefit possible. Presented below is an example table of study conditions.

Conditions will be counterbalanced across participants to control for order effects.

	Week 1	Week 2	Week 3	Week 4	
Expecting	Adderall	Adderall	Placebo	Placebo	
Medication	Adderall	Placebo	Placebo	Adderall	

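### Pregnancy is an exclusion but is tested only at screening, and the protocol secures no pregnancy question or test before the pill at the four later weekly doses

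*Protocol*

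**What the plan says.** Section 4.2 of the protocol lists "Pregnant/breastfeeding" among the exclusions. Section 4.3 applies this at the screening appointment: "A pregnancy test will be obtained for all non-sterile female participants". A positive result disqualifies at once, and results are to be read "prior to giving any medication to a subject". The same section then says that the pregnancy test and the urine drug screen "will not be repeated during the study unless considered clinically necessary based on history or signs and symptoms at the discretion of the study physicians".

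Section 3.1 puts every participant through four conditions, one a week for four weeks. The Study Summary gives one morning dose at each imaging visit, either Adderall 10 mg or placebo.

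Section 6 states the dosing condition at each visit: "If pulse and blood pressure are within acceptable limits, medication will be administered". It also says: "The MRI safety questionnaire will be reviewed and signed at each scanning visit". And: "Any abnormal findings will be discussed with physician investigator who will determine if the subject is fit to participate in the study". The other stated pre-dose steps are the mood scale and a self-rating of mental acuity. The side effect checklist is reviewed after the dose.

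**The concern.** The protocol treats a pregnancy result before dosing as necessary, but applies this only ahead of the first dose. One result then serves four dosing visits, and its age at the first of them is not bounded. The exception that allows a retest depends on history, signs or symptoms reaching a study physician. The visit text names no step before the pill that would collect a pregnancy history. Section 7.4 has the physician on call during imaging sessions, so someone must first raise the question.

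What is at stake is participant safety: giving Adderall to someone who now meets a named exclusion, without any departure from the written procedure. The primary endpoint in section 3.2, feasibility and acceptability, is not affected.

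**Working it through.** There is no plan figure to reproduce. The check is a comparison of sections and a count.

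**Inputs**
- Scheduled pregnancy tests: 1, at screening; routine repeats: 0 (section 4.3).
- Dosing visits: 4, one a week (sections 3.1 and 6).
- Conditions: drug given (Adderall or placebo) crossed with truth or deception (section 3.1).
- Dose: 10 mg per active visit (Study Summary).
- Limit on the time from screening to first dose: none stated.

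**Active doses per participant.** Two of the four cells contain Adderall: 2 × 10 mg = 20 mg in total.

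**Age of the test at the last active dose.** The protocol does not list the orders used, so take all possible ones: 4! = 24. The two Adderall weeks can be chosen in 6 ways, and each choice corresponds to 2! × 2! = 4 orders.

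| Last Adderall week | Orders | Age of the test, beyond the screening-to-week-1 gap |
|---|---|---|
| 4 | 3 × 4 = 12 | about 3 weeks |
| 3 | 2 × 4 = 8 | about 2 weeks |
| 2 | 1 × 4 = 4 | about 1 week |

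The orders sum to 24, so every possible order places an Adderall dose at least a week after the first visit, and half place one in week 4. The example table in section 6 is one of these: its week 4 is an Adderall week.

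**What stands between a new pregnancy and the pill**
- *Pulse and blood pressure:* stated, and before the pill. They do not ask about pregnancy.
- *Mood scale and acuity rating:* stated, and before the pill. No pregnancy content is stated.
- *Side effect checklist:* after the pill.
- *MRI safety questionnaire:* reviewed at each visit, with abnormal findings going to the physician investigator. Section 4.3 gives its purpose as safety for scanning. Its items are not shown, and section 6 does not say whether it comes before or after the pill.
- *Physician-prompted retest:* available, but it needs a prompt.

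Only the questionnaire could supply that prompt routinely, and the text does not establish that it does so before dosing.

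**The case against.** The strongest reply is that section 4.3 records a deliberate choice. Positives are excluded at screening, a physician can order a retest, the dosing period is four weeks, and four participants are to complete. No other section contradicts the rule. All of this stands, and it is why the point is an inexpensive improvement and not an error. It does not answer the narrower point that the physician's discretion has no secured trigger before the pill.

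Four stronger readings are tempting, and the documents do not support them.

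- *That nobody asks about pregnancy at the visits.* The MRI safety questionnaire may well ask, and its findings go to a physician who judges fitness for the study, not only for scanning. The form is not shown, so its absence of a pregnancy item cannot be claimed.
- *That the risk can be given as a percentage.* The protocol gives neither a pregnancy rate nor a sex mix. An assumed 2% chance per woman, with four non-sterile women, would give 1 − 0.98⁴ = 7.8%; an assumed 0.1% would give 1 − 0.999⁴ = 0.4%; with no such women it is zero. These figures only restate the assumption. They also count pregnancy at any dosing visit, not exposure to Adderall: a conception late in the study may meet only placebo.
- *That the deception raises the risk.* In one of the two Adderall sessions the participant "will receive medication when they believe they are not receiving medication". She might then have less reason to mention a late period, but nothing in the protocol supports this, and it loses its force if a question is asked at every visit.
- *That stimulant use after enrolment goes unchecked.* The retest exception covers the drug screen too, and the disqualification rule can reasonably be read to cover a prompted repeat. The pulse and blood pressure check gives some further protection.

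**Conclusion.** The point holds in a limited form. Pregnancy is an exclusion tested once, routine repeats are ruled out, and the visible text secures no pregnancy question before any of the four study doses. A participant who becomes pregnant after screening could receive up to two 10 mg Adderall doses with the protocol followed as written. Two doses is the worst case.

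This rests on the visible text alone. If the MRI safety questionnaire already asks about pregnancy and is completed before the pill, the missing question is answered in practice, and what remains is to say so in the protocol. The absolute risk is small and cannot be quantified from the protocol. This is a safety improvement worth making because it is cheap; it is not a defect in the design or its endpoint.

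**What to change.** Amend section 4.3 and the visit text in section 6 so that, at every dosing visit and before the pill:

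- non-sterile female participants answer a pregnancy question, and the answer is recorded. The MRI safety questionnaire may serve if it has this item and the protocol says it is completed before dosing;
- they have a urine pregnancy dip, or at minimum a dip whenever the answer is positive or uncertain;
- the pill is withheld until any dip result is read.

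A routine dip should be done at all four visits, because dips only at Adderall visits would break the blind. Physician discretion over other repeat tests can stay as it is.

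The cost is about two sentences of protocol text and a few minutes per visit. Routine dips come to 4 per non-sterile female completer, so 0 to 4 × 4 = 16 among four completers, plus one for each visit attended by such a participant who is later replaced. The minimum version needs far fewer. A late disqualification is possible and would use one of the six alternates. A dip cannot exclude a very recent conception, so it reduces the exposure without removing it.

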4.4 Early Withdrawal of Subjects

4.4.1 When and How to Withdraw Subjects

Students will be informed they may withdraw from the study at any time, for any reason, before it is completed. They will be informed that their participation will not affect their class standing or grades at UAB. They will not be offered or receive any special consideration if they take part in the research. Employees will be informed that taking part in the research is not part of their UAB duties and refusing to be a part of the study will not affect their job or relationship with UAB. They will not be offered or receive any special job-related consideration if they take part in this research.

5. Study Drug

Dextroamphetamine-amphetamine & Placebo

6. Study Procedures

Study Appointment (2-3 hours): Pulse and blood pressure will be measured before medication is administered. If pulse and blood pressure are within acceptable limits, medication will be administered. A potential side effect checklist (attached) will be reviewed after the period of time in which medication effects would become active. Any reported side effects will be addressed prior to continuation of the session. The MRI safety questionnaire will be reviewed and signed at each scanning visit. This questionnaire will be filed at the CINL. Any abnormal findings will be discussed with physician investigator who will determine if the subject is fit to participate in the study.

The participant will be given either a placebo or Adderall depending on randomization. Each participant (N = 4) will either be told that he/she is receiving Adderall or placebo, as indicated on pre-labeled medication bottles to preserve the double-blind nature of the study. The participant will either receive medication or placebo as they are informed, not receive medication when they believe they are receiving medication, or will receive medication when they believe they are not receiving medication. This will allow for measurement of expectancy, which is a core measure for this study. This study design makes the comparison of cognitive performance based on actual versus perceived benefit possible. Presented below is an example table of study conditions.

Conditions will be counterbalanced across participants to control for order effects.

	Week 1	Week 2	Week 3	Week 4	
Expecting	Adderall	Adderall	Placebo	Placebo	
Medication	Adderall	Placebo	Placebo	Adderall	

(Expecting refers to whether participants are told that they are taking Adderall or a placebo pill. Medication refers to the pill that participants are actually receiving.)

Before the medication is administered and after the MRI scan, participants will complete the POMS (Profile of Mood States) to measure mood and euphoria (attached). Participants will also self-report on their perceived mental acuity pre-dose and after each cognitive task (described below) performed in the scanner on a scale of 0-100with 100 indicating "more sharp than normal."

Cognitive testing will be timed to begin 45 minutes after medication or placebo is given.

Participants will then start the magnetic resonance spectroscopy scanning portion of the session, which will take one hour. The MRI scan will not include the use of a contrast agent. A 3 Tesla Siemens Prisma scanner and 20-channel head coil will be used. Scan sequences are listed below:

- Auto-align scout (1 min): to determine brain orientation and slice prescription. Will use 260mm field of view (FOV), 160 x 160 matrix, 3.15ms repetition time (TR), 1.37ms echo time (TE), 1.6mm slice thickness, no gap. The scout data are not used in post-scan analyses, so processing and analysis steps are not described.
- T1-weighted magnetization prepared rapid gradient echo (MPRAGE) high-resolution scan (10 min): for anatomical localization and to achieve standard space for group analyses.
 Will use 230mm FOV, 256 x 256matrix, 2000ms TR, 2.51ms TE, 0.9mm slice thickness, and no gap, yielding 0.9x0.9x0.9mm voxels.
- Functional MRI (60 min): Axial T2*-weighted images will be acquired using an echoplanar sequence 220x220 FOV, 64x64 matrix, 2000ms TR, 28ms TE, 3mm slices, yielding 3x3x3 mm voxels. Heart rate and respirations will be measured continuously in the scanner.
 - Participants will complete a "resting state" scan in which they are instructed to close their eyes and rest.
 - While undergoing fMRI scans, participants will complete three different cognitive
 tasks measuring aspects of sustained attention, new learning, and working memory.
 Participants will receive a short explanation of each task, as well as sample items,
 prior to entering the scanner, and will be able to have their questions answered.
 Specific task instructions will also be presented on screen inside the scanner prior to
 each task.
 - The first task will utilize a paced serial addition paradigm. Participants will be

presented with a string of single digits (0-9), one every three seconds, for approximately 12 minutes. The digits will be presented in auditory form via headphones. Participants will be asked to add the two most recently presented digits in their mind, and will respond with a button press each time the two digits add up to 10. The task does not require participants to maintain a running total of all digits, meaning that participants can resume the task at any point in case of set loss. We will measure the accuracy of participants' responses.

- During the second task, a sustained attention task, a row of 5 left- or right-pointing arrows will be presented on each trial. The participant will be required to indicate the direction of the central arrow (left or right) by pressing one of two buttons. The target arrow in the center of the row will be flanked by two non-target stimuli on either side, which point either in the same direction as the target, the opposite direction, or will be circles. The row of arrows will be presented in rapid succession and the participant is to indicate their response as quickly as possible on each trial by pressing the button. The task will last no longer than 15 minutes.
- During the final task, a visual version of a paired associates learning task, participants will be presented with 50 word pairs on screen, and will be asked to memorize both words in each pair. The pairs will be presented individually, at a rate of one word pair per three seconds. The 50 word pairs will be presented three times in the same order, for a total of 7 minutes and 30 seconds. Words in each pair will be everyday objects of neutral emotional valence, and will be limited to 8th grade reading level (e.g. rose bag; elephant glass). fMRI scans will be acquired during the learning phase of this task, although no response is required from participants during this time. Immediately following completion of the learning phase, participants will be presented with the first word from each pair on screen, and will be asked to name the second word in the pair. No brain scans will be acquired during the recall phase, but the accuracy of participants' responses will be recorded by a member of the research team.
- Each task will take no longer than 15 minutes to complete, and participants will be given short periods of rest between tasks, as needed. Participants will not receive feedback about the accuracy of their performance.

After the MRI portion of the session is complete, an additional neuropsychological battery will be administered to participants:

Repeatable Battery for the Assessment of Neuropsychological Status (RBANS): Measures various domains including immediate and delayed memory, visuospatial/constructional, language, and attention

Debriefing: After all four weeks of the protocol, a research assistant will conduct the debriefing portion of the session to inform participants about the deception aspect of the study. Following a manipulation check, the research assistant will disclose whether the participant received Adderall or placebo during each session. The research assistant will discuss the participants' feelings

about the deception, use this as a chance to educate them about cognitive enhancers, and more fully explain the reasons for doing the study. Participants will be given as much time as deemed clinically appropriate to answer all questions and concerns or address any feeling of betrayal in an accepting way.

Prior to leaving, the side effect checklist will be completed a final time and blood pressure and pulse rechecked by trained study staff. Stable subjects will be allowed to leave. Any subjects experiencing side effects will be observed longer, or in the rare event of more moderate to severe adverse events (most commonly hypertension < 160/110), will be referred to the ER at the discretion of the physician and PI. Orange juice will be kept on site for use in subjects experiencing negative symptoms, as acidifying urine increases amphetamine excretion. A study physician will be available at all times.

7. Safety and Adverse Events

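### The side effect checklist has no pre-dose reading at any visit, so a symptom present on arrival is hard to tell from one that began after the pill (minor)

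*Protocol*

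**What the plan says.** Protocol section 6 (Study Procedures) sets the order of a visit. Vital signs come first: "Pulse and blood pressure will be measured before medication is administered". Medication or placebo follows, with the participant told which it is, truthfully or not, from a pre-labelled bottle. Then comes the checklist: "A potential side effect checklist (attached) will be reviewed after the period of time in which medication effects would become active". Its results are acted on: "Any reported side effects will be addressed prior to continuation of the session". The only other use described is at exit: "Prior to leaving, the side effect checklist will be completed a final time and blood pressure and pulse rechecked by trained study staff". That sentence follows the debriefing paragraph, so it is not fully clear whether it applies to every visit or only the last. Either way it comes after dosing.

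Two self-reports do have a pre-dose value. On mood: "Before the medication is administered and after the MRI scan, participants will complete the POMS (Profile of Mood States) to measure mood and euphoria (attached". On acuity: "Participants will also self-report on their perceived mental acuity pre-dose and after each cognitive task".

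The screening instruments in section 4.3 do not include the checklist: "Participants will then fill out a demographics sheet, MRI Safety Questionnaire, Prescription Stimulant Expectancies Questionnaire (PSEQ-II), and an ADHD screener", the last being the ASRS. Medical and psychiatric history is also reviewed at screening. Section 7.2 has all adverse events documented and summarised annually and at study end. Neither 7.2 nor 7.3 separates symptoms present before a dose from those that start after it.

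**The concern.** Many of the side effects listed in section 7.1 are everyday complaints: nervousness, headache, drowsiness, dizziness, restlessness, dry mouth, loss of appetite, trouble sleeping. A student may arrive with one of them. If the form is first used once the pill is expected to be active, such a complaint and a new one look alike on paper.

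This design adds to the difficulty, because the participant has by then been told Adderall or placebo, and the study exists to measure what that message does. A participant asked afterwards whether a headache was there earlier answers knowing the label. Only a reading taken before the label is free of that influence.

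At stake is how well single events can be attributed, and how cleanly tolerability can be described in a study whose primary endpoint (section 3.2) is feasibility and acceptability. A baseline that was not collected cannot be recovered by any later analysis.

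**Working it through.** The protocol gives no figure to reproduce. The check is first a comparison of timings, then an illustration of size.

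**Timings at a study visit (section 6)**

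| Measure | Before dosing | After dosing |
|---|---|---|
| Pulse and blood pressure | yes | yes, before leaving |
| POMS | yes | yes, after the scan |
| Self-rated acuity | yes | yes, after each task |
| Side effect checklist | none described | yes, once effects are expected, and before leaving |

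The checklist is the only repeated participant measure of this kind without a pre-dose value. The POMS is described as covering mood and euphoria. It may overlap with nervousness or restlessness, but not with headache, nausea or dry mouth.

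**Number of sessions**

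- Participants: 4 (section 6).
- Conditions per participant: 4, two with Adderall and two with placebo (sections 3.1 and 6).
- Total sessions: 4 × 4 = 16. Active sessions: 4 × 2 = 8.

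**Illustration**

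Let p be the chance that a session starts with at least one listed symptom that lasts until the first checklist. The protocol gives no value, so p = 5% to 40% is purely an assumption.

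- Expected affected active sessions, 8p: 8 × 0.05 = 0.4; 8 × 0.10 = 0.8; 8 × 0.20 = 1.6; 8 × 0.40 = 3.2.
- Expected affected sessions overall, 16p: 0.8; 1.6; 3.2; 6.4.
- Chance of at least one affected active session if sessions are independent, 1 − (1 − p)^8: 34%; 57%; 83%; 98%.

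The expected counts do not need independence, but the last line does. If the same people always arrived with symptoms, the exponent would be 4, the number of participants. The range would then be 1 − 0.95^4 = 19% to 1 − 0.60^4 = 87%.

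**The case against.** - **The form is not shown.** It is an attachment and may ask when a symptom began. This stands. A reader might infer that arrival symptoms are definitely recorded as effects of the pill, but the text says only that the checklist is reviewed and reported side effects are addressed. The narrower point remains: an onset question asked after the label is not equivalent to a reading taken before it.
- **Placebo sessions are a control.** This also stands. Every participant has two sessions of each kind in counterbalanced order, so arrival symptoms should fall on both. A reader might infer that the Adderall-placebo comparison of side effects is biased. The design does not support that: on average it need not be. Nor is the control merely a contrast between groups, since it is within person. It still cannot say whether one headache in one session was new.
- **Reporting is mostly in summary.** Section 7.2 reports adverse events in summary form. Only unanticipated and serious events are reported individually (section 7.3). A reader might infer that every arrival complaint becomes an individual report, and the text does not say so.
- **The checklist works as a safety step.** Acting on a symptom whatever its cause is cautious, and abnormal findings go to a physician investigator. That the step may be triggered by a symptom brought to the visit is no harm and no part of this point.
- **The endpoint does not name checklist counts.** True. Tolerability is a natural part of acceptability, but the protocol does not define it that way, and section 10 does not anticipate publication. This limits the weight of the point.
- **A pre-dose form does not isolate the scanner.** Nervousness that grows as the scan nears would still count as new. That is right, and the placebo sessions are what separate it out.

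**Conclusion.** The point holds as a minor, inexpensive improvement. Followed as written, the protocol collects no pre-dose checklist reading at any visit, although it collects a pre-dose value for the comparable measures. The consequence is weaker attribution of individual events and added noise in the tolerability description, which four participants cannot average out. It is not a bias in the average Adderall-placebo comparison.

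The size is illustrative: 0.4 to 3.2 of the 8 active sessions, for an assumed 5% to 40% arrival prevalence and symptoms that persist to the checklist. The conclusion that a pre-dose reading is missing does not depend on that range. How much is lost does, and it also depends on whether the attached form asks about onset.

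**What to change.** In section 6, add a use of the same checklist at every session before dosing and before the label is disclosed, alongside the pre-dose pulse and blood pressure. Describe post-dose items as new or worse relative to that session's pre-dose answers, and report them next to each participant's own placebo sessions. The descriptive rule may sit in the analysis plan, but the extra reading has to be in the protocol. Leave unchanged the rule that any reported symptom is addressed before the session continues.

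The cost is one more use of an existing form, an estimated two minutes per session, or 16 × 2 = 32 minutes over the study. The downside is one more exposure to the symptom list, which could prompt some reports. It would occur in all four conditions alike.

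### Do the 3 mm functional voxel and the one-hour scan call for a change, when the figures printed beside them give 3.44 mm and 71 minutes?

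*Protocol*

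**What the plan says.** All the figures are in section 6 (Study Procedures) of the protocol.

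- **Functional scan:** "220x220 FOV, 64x64 matrix, 2000ms TR, 28ms TE, 3mm slices, yielding 3x3x3 mm voxels". No unit is printed for the field of view; the other two sequences give theirs in millimetres.
- **Structural scan:** "230mm FOV, 256 x 256matrix, 2000ms TR, 2.51ms TE, 0.9mm slice thickness, and no gap, yielding 0.9x0.9x0.9mm voxels". This is the only other sequence with a stated voxel size.
- **Length of scanning:** "Participants will then start the magnetic resonance spectroscopy scanning portion of the session, which will take one hour". The sequences then listed are labelled "Auto-align scout (1 min", "high-resolution scan (10 min" and "Functional MRI (60 min" (each label is cut before its closing bracket).
- **Visit and timing:** "Study Appointment (2-3 hours): Pulse and blood pressure will be measured before medication is administered" gives the length of the visit, and "Cognitive testing will be timed to begin 45 minutes after medication or placebo is given" gives the only time anchor after dosing.

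Section 3.2 makes feasibility and acceptability of the imaging the primary endpoint. Section 10 says that, given the small sample, publication is not expected.

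**The concern.** Each of the two lines supplies the inputs to a simple sum and then prints a different answer. The functional line presents its voxel size as the result of the field of view, matrix and slice thickness, but those entries do not give 3 mm in-plane. The scanning portion is given one hour, but the functional block alone is labelled with the whole hour, which leaves no room for the scout and the structural scan.

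Two things could be at stake. A wrong acquisition specification could mean that the images are not those the protocol describes. And because the trial tests whether this imaging is feasible and acceptable, a scanning time that is understated could bear on the endpoint itself, or on whether the visit can hold everything planned for it.

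**Working it through.** **Voxel size.** In-plane size = field of view / matrix.

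| Sequence | Field of view (mm) | Matrix | Computed (mm) | To one decimal | Printed in the protocol |
|---|---|---|---|---|---|
| Scout | 260 | 160 | 1.625 | 1.6 | no voxel size; slice 1.6 |
| Structural | 230 | 256 | 0.898 | 0.9 | 0.9 |
| Functional | 220 (mm assumed) | 64 | 3.4375 | 3.4 | 3 |

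The rule reproduces the structural figure and agrees with the scout's slice thickness. It reproduces the functional figure only after rounding to a whole millimetre.

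- Volume from the printed inputs: 3.4375² x 3 = 35.45 mm³.
- Volume as stated: 3³ = 27 mm³. Ratio: 35.45/27 = 1.31.
- An exact 3 mm would need a field of view of 3 x 64 = 192 mm with this matrix, or a matrix of 220/3 = 73.3 with this field of view. The protocol does not show which entry is off.

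**Scan length.** Sum of the labels: 1 + 10 + 60 = 71 min, against 60 min stated. The excess is 11 min, or 11/60 = 18%. If the hour is right, the functional block has 60 - 11 = 49 min. No spectroscopy sequence is listed, although the sentence names one; 71 min is the total of what is listed.

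**Do the tasks show which label is wrong?** Printed task times are about 12 min, at most 15 min, and 50 x 3 x 3 s = 7.5 min for the learning phase: 12 + 15 + 7.5 = 34.5 min. The only firm limit common to all three tasks is 15 min each: 3 x 15 = 45 min.

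| Functional block | Left after 34.5 min | Left after 45 min |
|---|---|---|
| 49 min | 14.5 min | 4 min |
| 60 min | 25.5 min | 15 min |

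The remainder must hold the resting-state scan, whose length is not given, together with ratings, instructions, rests and, in the 34.5-minute column, recall. The task times therefore do not decide between the two figures.

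**Does the visit hold the scan?** This depends on how the 45-minute anchor is read.

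- If scanning starts 45 min after dosing, it ends at 45 + 71 = 116 min, or at 45 + 60 = 105 min with a one-hour scan. A 120 to 180 min visit then leaves 4 to 64 min, or 15 to 75 min, for everything else.
- If the 45 min marks the first task in the scanner and the scans run in the listed order, scanning starts at least 11 min earlier, at 34 min or before. It then ends by 34 + 71 = 105 min.
- If testing starts at 45 min and scanning follows it, as the word order suggests, scanning ends later than in the first case.

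The pre-dose checks, mood scale, RBANS and final checks have no stated durations, so the protocol shows neither that the visit fits nor that it does not.

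**What uses these numbers?** The protocol defines no outcome that depends on voxel size. Section 3.2 sets no threshold on scan duration. The in-scanner measures named are accuracy and self-rated acuity. One scan procedure is described for all four sessions, so a misprinted specification applies equally to each condition.

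**The case for a change.** The case for acting is that rounding is a weak excuse. The structural line is given to one decimal, and at that precision the functional voxel is 3.4 mm. The wording makes the voxel a product of the acquisition settings, so a resampled size does not fit either, and the printed result is a cube that the inputs do not produce. On time, reading the hour as the functional block alone means ignoring two sequences listed under it. The study is about the feasibility of this imaging, so scanning time is part of what is being tried. On one reading, the two-hour visit is left with only 4 min for all other procedures. The edit would also be cheap.

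The arithmetic in this case stands in full, and no other part of the protocol removes either mismatch. The weight placed on it does not stand. A 0.9 mm voxel cannot usefully be written in whole millimetres, whereas the functional line gives its slices in whole millimetres, so differing precision between the lines is plausible. The functional bullet also covers rests and a recall phase that is not scanned, so its label need not be pure acquisition time. The 4-minute margin belongs to one reading of the timing and to the short end of a 2-3 hour range; the long end leaves 64 min. The link to the primary endpoint is thin, because nothing in it is scored by minutes in the scanner. A cheap edit is worth requiring only if something depends on it, and here nothing is shown to.

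**Conclusion.** The two discrepancies are genuine and clerical: 3.44 mm against 3 mm in-plane (volume ratio 1.31), and 71 min against 60 min for the scanning portion. No change to the plan follows. No bias between conditions, no infeasibility and no effect on any defined outcome or conclusion is shown. The trial has four completers and aims at feasibility and acceptability. Staff who run the scanner can settle both figures from its exam card and can tidy the wording whenever the protocol is next edited.

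This rests on three assumptions: that the functional field of view is in millimetres, that every session uses the same sequences, and that no analysis outside the protocol depends on the stated voxel size. If an imaging analysis were planned that took 3 mm as the acquired resolution, the voxel line would need to be reconciled first.
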